## 12.3 Sample Size and Accrual

At the Fred Hutch, we perform approximately 250 allogeneic transplants per year, approximately 5% of which involve umbilical cord blood donors. We also perform approximately 180 autologous transplants per year. The target enrollment for this trial is approximately 50 HCT candidates, of which ten participants will be autologous HCT candidates and 40 will be allogeneic HCT candidates (including cord blood HCT candidates). At least 8 of the allogeneic HCT candidates will be from HLA-mismatched (related or unrelated) HCT recipients. Based on the estimated number of treated patients per year (and previously treated patients since 2013), as well as the estimated number of patients that we may enroll (i.e., ‘feasible’ patients) after accounting for estimated eligibility and consent rates, it will be feasible to enroll approximately 55 subjects over 6-12 months. Our final estimated sample size will be 50 subjects after accounting for an estimated 10% dropout prior to completion of the full 24-week study period. If the dropout rate is higher at three months after mAb infusion, we may enroll more patients to achieve a target of 50 overall subjects. The study is open to anyone regardless of gender or ethnicity. Efforts will be made to extend the accrual to a representative population. If accrual is slow, we may add another site. If accrual of the HLA-mismatched strata is slow, we may analyze and report the results in the HLA-matched strata once that is fully enrolled given the urgency of the pandemic.

- Primary objective: Our primary endpoint is to calculate the half-life of VIR-7831 post-transplant. Based on the half-life seen with other antibodies containing the LS mutation in adults who have not undergone transplant, we anticipate a half-life of up to 3 months. However, this half-life may be shortened in transplant recipients. Since we will use descriptive statistics, the sample size is

sufficient to provide data to calculate the half-life. Levels of VIR-7831 can be measured using an idiotypic antibody assay that is not affected by COVID-19 infection or vaccination.

- Secondary and exploratory objectives: We anticipate enrolling ten autologous HCT candidates. We anticipate enrolling approximately eight HCT candidates receiving HLA-mismatched (related or unrelated) transplants. This will serve as pilot data to examine whether HLA-mismatch affects the half-life of VIR-7831. To compare antibody levels between venipuncture vs TASSO and nasal swab in the first month of the study, we will have at least  $4 \times 50 = 200$  specimens in each group. Based on the phase 3 COMET-ICE study, we do not anticipate any adverse effects or safety signals. Although there is currently no data available on the use of VIR-7831 as prophylaxis, it is possible we may observe breakthrough infection with SARS-CoV-2, particularly towards the end of the study as antibody levels wane.

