**Biomarker Assessments:** Immediately prior to mAb administration and at the end-of-infusion, weekly up to week 4, monthly up to week 12, and at week 24 after mAb administration, blood will be drawn by venipuncture (10-20 mL per blood draw) by nursing, a phlebotomist, or trained study staff. At week 12, and monthly thereafter to the end of primary end-point (week 24), blood is self-collected using a TASSO device and by venous blood draw. Nasal specimens will be collected by mid-nasal foam swab at the same time-points as blood draws. Nasal swabs and blood via TASSO (or venous blood draw) will also be collected off-schedule for SARS-CoV-2 PCR and antibody testing as needed based on respiratory symptoms (answering yes to one or more of the nose or chest symptoms) within 48 hours of symptom of symptom onset, up to week 36. If positive for SARS-CoV-2, weekly nasal swabs will be obtained longitudinally for SARS-CoV-2 PCR until negative or until week 36. Serum, plasma, or nasal swabs will be processed and stored at either 4°C, at -20°C, or at -70°C until use, as appropriate. Testing will include serum and nasal total IgG, VIR-7831, SARS-CoV-2-specific IgG, SARS-CoV-2 neutralization titers, and anti-drug antibodies. Testing will be performed at the Fred Hutch, UW, or by Vir Biotechnology.

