## 4.1 Overall Study Design

**Figure 1: Overview of study design and timeline.**

Participants will be screened, consented, and enrolled prior to transplant. Clinical evaluation will occur immediately prior to mAb administration. Participants will complete a weekly symptom questionnaire prior to and weekly after mAb administration for a total 36 weeks. Safety assessments will be performed with routine labs as part of standard stem cell transplant care. mAb will be administered intravenously within seven days of the start of conditioning, and the mAb will be infused at least 24 hours prior to the start of conditioning, i.e. mAb infusion will occur within 1-7 days prior to conditioning. Immediately prior to mAb administration (Pre), at the end-of-infusion (\* in the schematic), weekly up to week 4, monthly up to week 12, and at week 24 after mAb administration, blood will be collected by venipuncture or from a central venous catheter if one is available (10-20 mL per blood draw). At week 12, and monthly thereafter to the end of the primary end-point (week 24), blood will be self-collected using a TASSO device if the participant is unable to return for a venous blood draw. Each timepoint for blood collection will utilize two TASSO devices (or one TASSO+ device). If a participant can present in clinic or is in the hospital, blood collection by venipuncture or from a central venous catheter is permitted instead of using a TASSO device. Nasal specimens will be collected by mid-nasal foam swab at the same time-points as blood draws for antibody testing. Additional nasal swabs may also be collected off-schedule as needed based on reporting of respiratory symptoms on the weekly questionnaire, up to week 36. If positive for SARS-CoV-2, weekly nasal swabs will be obtained longitudinally for SARS-CoV-2 PCR until negative or until week 36. If a participant can present in clinic or is in the hospital, blood can be collected by venipuncture or from a central venous catheter instead of by a TASSO device. Routine nasal swabs collected as part of standard clinical care for SARS-CoV-2 surveillance by PCR post-transplant are not shown. At week 36 (not shown), participants will receive a follow-up phone call to assess for the development of antibody dependent enhancement if they had COVID-19.

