### **Research samples:**

- 1) Blood: All blood specimens are collected for the PK, neutralization, and IgG assays. Immediately prior to mAb administration, at the end-of-infusion, weekly up to week 4, monthly up to week 12, and at week 24 after mAb administration, blood will be collected by venipuncture (10-20 mL per blood draw). Blood drawn from a central venous catheter is permitted. Blood from venipuncture or a central venous catheter will be collected by inpatient nursing, outpatient nursing, phlebotomy, or the study team. If the participant is unable to return to the clinic or hospital for their last blood draw (week 24), we may provide a kit including blood collection tubes so a blood draw can be performed at the participant's local phlebotomy clinic or lab and shipped back to the study site. At week 12, and monthly thereafter to the last blood draw (week 24), blood will be by venous blood draw and self-collected using a TASSO-SST or TASSO+ device. The Tasso™ (Tasso Inc., Seattle WA) device is optimized for needle-free self-collection of blood at home. The TASSO-SST and TASSO+ devices can collect up to 300 µL and 600 µL, respectively, of whole blood from capillaries that can be spun down to serum. For each TASSO time-point, blood will be collected in either two TASSO-SST devices or one TASSO+ device. Each participant will be provided with a backup TASSO device for each TASSO collection time-point in case of device failure (expected 15% failure rate). We have experience using this technology with ongoing COVID-19 antibody testing studies at FHCRC (249 subjects and 2,289 devices). According to the manufacturer, the device has been used in over 5000 subjects since 2004 without any known severe events. The risk for participants is minimal and comparable to the procedures (lancing) for monitoring blood sugar levels. Additional blood may also be collected off-schedule as needed based on reporting of respiratory symptoms (one or more nose or chest symptoms) on the weekly questionnaire (if a specimen is not already scheduled to be collected within a week) for PK, neutralization, and IgG assays. Additional blood samples may also be requested due to inadequate collection or issues related to mail service delivery. Samples will be processed and stored at -20°C or -70°C until use, as appropriate.

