## 12.2 Secondary Objectives

- Secondary and exploratory objectives: We will compare antibody levels in autologous vs. allogeneic transplant, cord vs. non-cord allogeneic transplant, matched vs. mismatched transplants, in patients with and without GVHD, and in patients with and without diarrhea to test if HLA-mismatching, GVHD, and/or diarrhea are associated with accelerated antibody decay. Diarrhea will be assessed on the weekly questionnaire and the presence/severity/tissue involvement of GVHD will be assessed by review of the medical record at all timepoints indicated in Figure 1. We will also compare antibody levels from serum collected by venipuncture versus self-collected using a TASSO device and from fluid collected by nasal swabs. Based on preliminary and published data, we expect a high concordance between antibody levels from capillary blood collected by TASSO and venous blood collected by venipuncture or from a central venous catheter. If there is a slight discrepancy, we can calculate a correction factor based on the results from the paired specimens collected on week 12. If there is an unexpected significant discrepancy between antibody levels that cannot be corrected, we will have a venous blood draw at week 24 to calculate half-life using just venous blood samples. We will monitor for breakthrough SARS-CoV-2 infection by PCR of fluid collected by nasal swabs. If breakthrough infection does occur, we may sequence the spike gene (or entire viral genome) to determine the variant and identify possible resistance mutations. We will also measure anti-drug antibodies in case this is correlated with half-life. We will also monitor routine safety labs as part of standard post-transplant care. Comparisons will be tested using a t-test. As part of an exploratory analysis, we may also calculate the half-life of VIR-7831 and of SARS-CoV-2 neutralizing antibodies in nasal swabs and of SARS-CoV-2 neutralizing antibodies in serum after infusion of VIR-7831.

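### Section 12.3 counts 200 TASSO specimens in the first month, but scheduled TASSO collection starts at week 12, and the sections disagree on whether TASSO and venous blood are paired

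*Combined protocol and SAP*

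**What the plan says.** **Stated size.** Section 12.3, under secondary and exploratory objectives, begins "To compare antibody levels between venipuncture vs TASSO and nasal swab in the first month of the study" and then gives at least 4 × 50 = 200 specimens in each group.

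**When TASSO is collected.** The synopsis (Biomarker Assessments), Section 4.1 and Section 9.1 (Research samples) each start scheduled TASSO collection at week 12 and continue it monthly to week 24.

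**Text that pairs the two samples.**
- Synopsis, for week 12 and monthly after: "blood is self-collected using a TASSO device and by venous blood draw".
- Section 9.1: "At week 12, and monthly thereafter to the last blood draw (week 24), blood will be by venous blood draw and self-collected" by TASSO.
- Section 2 describes venipuncture and TASSO collection as paired, and gives this as the way to learn whether TASSO results need correcting.
- Section 12.2: "we can calculate a correction factor based on the results from the paired specimens collected on week 12".

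**Text that makes one sample replace the other.**
- Section 4.1, for the same visits: "blood will be self-collected using a TASSO device if the participant is unable to return for a venous blood draw".
- Section 4.1, for participants in clinic or in hospital: "blood collection by venipuncture or from a central venous catheter is permitted instead of using a TASSO device". Appendix A, footnote D, gives the same permission.

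**Analysis.** Section 12.2 says that comparisons use a t-test. It does not say whether the test is paired or how repeat visits are handled. If the two methods disagree beyond correction, the fallback is "we will have a venous blood draw at week 24 to calculate half-life using just venous blood samples".

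**The concern.** The comparison of TASSO with venous blood is secondary objective 3. It also decides whether TASSO levels can be used, with or without a correction factor, once patients are followed less closely after day +100 (Section 2). What it needs is a known number of subjects who give both samples at the same visit.

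The plan does not supply that number. The 200 is tied to a month in which no TASSO sample is scheduled. It also counts specimens rather than pairs or subjects. The collection rules then differ by section. Staff who follow Section 4.1 to the letter would take one sample or the other at week 12, would be within the protocol, and would lose the pairs that Section 12.2 relies on. A missed week-12 pair cannot be recovered later.

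**Working it through.** **Inputs**
- Subjects: 50 (Section 12.3), taken here with complete sampling.
- Venous draws after infusion: weeks 1, 2, 3, 4, 8, 12 and 24 (the fixed schedule in the synopsis and Sections 4.1 and 9.1).
- Nasal swabs: at the same time-points as blood draws (Section 9.1).
- TASSO: week 12 and monthly to week 24. With the visit days in Appendix A, footnote C, these are days 84, 112, 140 and 168, i.e. weeks 12, 16, 20 and 24.

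**Step 1. Reproduce the stated figure.** Specimens = scheduled time-points in the window × subjects.

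| Group | Time-points in month 1 | Specimens |
|---|---|---|
| Venous | 4 (weeks 1–4) | 4 × 50 = 200 |
| Nasal | 4 (weeks 1–4) | 4 × 50 = 200 |
| TASSO, scheduled | 0 | 0 × 50 = 0 |

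The multiplication is right, and the figure holds for venous and nasal samples. Adding the pre-infusion and end-of-infusion samples gives 6 × 50 = 300, which still meets a minimum of 200. The figure fails only for TASSO.

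**Step 2. Where 200 TASSO specimens could come from.** Four visits over weeks 12 to 24 give 4 × 50 = 200 at most. These would be four repeats from each of 50 subjects, not 200 independent observations.

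**Step 3. Count the TASSO/venous pairs.** Pairs = visits with both samples × 50.

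| Text followed | Visits with both | Pairs |
|---|---|---|
| Section 12.2: week-12 pairs | 1 | up to 50 |
| Fixed venous draws that coincide with TASSO: weeks 12 and 24 | 2 | up to 100 |
| Synopsis and Section 9.1: both samples monthly from week 12 | 4 | up to 200 |
| Section 4.1, read strictly | 0 | none assured |

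In the last row, a participant who gives the venous sample does not meet the condition for TASSO, and one who uses TASSO has given no venous sample.

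**Step 4. Check whether the pairing text is itself consistent.** It is not. The synopsis and Section 9.1 each list venous draws monthly to week 12 and then at week 24, and then call for venous blood plus TASSO monthly from week 12. Venous draws at weeks 16 and 20 are therefore in doubt, which is the difference between 100 and 200 pairs. Section 12.2 in turn presents the week-24 venous draw as a contingency, although the synopsis and Sections 4.1 and 9.1 schedule it.

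**The case against.** The best defence is that the first-month phrase in Section 12.3 belongs to the nasal swabs alone. TASSO's 200 would then be the four visits from week 12, and the error would be one loosely placed phrase. This is possible but strained, and it does not settle the size: on the fixed schedule only two of those four visits have a venous comparator.

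A second defence is that symptom-driven TASSO samples can fall in month 1. They can (synopsis), but their number is not given and cannot support a minimum of 200.

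Third, Section 4.1 does not stand alone. The synopsis and Sections 2, 9.1 and 12.2 all point to pairing, the replacement clauses are permissive, and footnote C allows for venipuncture, TASSO or both. This stands in part. A reader might infer that no pairs will be collected, and the documents do not support that: zero is the floor under one section read strictly, not a forecast. What remains is that the protocol lets a site skip the pair.

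Fourth, no power calculation, precision target or decision rule uses the 200. That is true and limits the weight of the count error on its own.

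Device failure might seem to lower the counts further. Section 9.1 supplies a backup device and adds "Additional blood samples may also be requested due to inadequate collection", so no reduction is applied here. A TASSO sample repeated on a later day would not clearly restore a same-visit pair, which is one reason why the counts are ceilings.

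**Conclusion.** The point holds. The scheduled first-month TASSO count is 0 against at least 200 stated; the venous and nasal counts stand. The number of TASSO/venous pairs is up to 50, 100 or 200 depending on the section followed, with none assured under a strict reading of Section 4.1. All of these assume 50 subjects with complete sampling; missed visits would lower them.

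Two stronger readings are not supported. A reader might infer that the primary half-life is undermined. It is largely protected, because venous draws are scheduled through week 12 and at week 24, and Section 12.2 has a venous-only fallback. A reader might also infer that pairs can come only from the 30 subjects still to be infused, because 20 had already been infused. The documents do not say whether those 20 have given, or can still give, a pair, and Section 12.3 allows extra enrolment if dropout at three months is higher than expected. No smaller count is claimed on that ground.

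This should be fixed as a matter affecting a secondary objective and the TASSO correction factor.

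**What to change.** 1. **Section 12.3.** Limit the first-month 4 × 50 = 200 to venous and nasal samples. Give the TASSO window as weeks 12 to 24. State the size of the TASSO/venous comparison as the number of subjects with a week-12 pair (up to 50), plus any later repeat pairs.
2. **Synopsis, Sections 4.1, 9.1 and 12.2, and Appendix A footnote D.** Reconcile these so that both samples are collected at week 12 whenever the participant attends. State whether venous draws are scheduled at weeks 16, 20 and 24, and when one sample may replace the other. Aligning Section 4.1 to the synopsis and Section 9.1 alone would not be enough, because those two are unclear on weeks 16 and 20.
3. **Section 12.2.** Replace the unspecified t-test for this comparison with a paired within-subject analysis that accounts for repeat visits.

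The cost is wording. Pairing at week 12 adds no sampling beyond what the synopsis and Section 9.1 already describe. New wording cannot create pairs for visits already completed, so the change is worth making promptly, and the sponsor should count the pairs in hand.

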## **13. DATA AND SAFETY MONITORING PLAN**

### **13.1 Overall Scope of Monitoring Activities**

Institutional support of trial monitoring will be in accordance with the FHCRC/University of Washington Cancer Consortium Institutional Data and Safety Monitoring Plan (DSMP). Under the provisions of this plan, the Principal Investigator will conduct continuous review of data and subject safety. FHCRC Clinical Research Support coordinates data and compliance monitoring conducted by consultants, contract research organizations, or FHCRC employees unaffiliated with the conduct of the study.

In addition, protocols are reviewed at least annually and as needed by the Consortium Data and Safety Monitoring Committee (DSMC), FHCRC Scientific Review Committee (SRC) and the FHCRC/University of Washington Cancer Consortium Institutional Review Board (IRB). The review committees evaluate accrual, adverse events, stopping rules, and adherence to the applicable data and safety monitoring plan for studies actively enrolling or treating patients. The IRB reviews the study progress and safety information to assess continued acceptability of the risk-benefit ratio for human subjects. Approval of committees as applicable is necessary to continue the study.

The trial will comply with the standard guidelines set forth by these regulatory committees and other institutional, state, and federal guidelines.

### **13.2 Monitoring the Progress of Trial and Safety of Participants**

The first level of trial oversight for this protocol will be provided by the Principal Investigator and the Research Coordinator(s) who will provide continuous oversight of the trial. These individuals will meet at least weekly to review recently acquired data and adverse events. Serious adverse events will be reviewed upon occurrence to ensure prompt and accurate reporting to the appropriate committees and regulatory agencies as described above. The data recorded in the research charts and protocol database will be compared with the actual data available from the medical record and/or clinical histories. Data detailed in the research case report forms (CRFs) will include the nature and severity of reportable AEs. The Principal Investigator and all other study team members on the protocol have received formal training in the ethical conduct of human research. The study team will at monthly intervals provide GSK with a report detailing the progress of the study including study site initiation and study subject

recruitment. The study team will also keep GSK apprised of the progress ethics committee submissions, approvals, and amendments.

## **14. DATA MANAGEMENT/CONFIDENTIALITY**

The investigator will ensure that data collected conform to all established guidelines for coding collection, key entry, and verification. Each subject is assigned a unique subject number to assure subject confidentiality. Information forwarded to regulatory agencies will refer to patients by a coded identifier and not by name. Subjects will not be referred to by this number, by name, or by any other individual identifier in any publication or external presentation. The licensed medical records department, affiliated with the institution where the subject receives medical care, maintains all original inpatient and outpatient chart documents. Additional clinical data may be made available from the Fred Hutch core database which is managed and verified independent of the research group.

The research team will maintain Case Report Forms (CRFs) and associated research documentation for each patient treated under the protocol. This documentation includes both clinical data and study-specific documents for each patient. The Principal Investigator or a designee will verify completed CRFs against source documentation on an ongoing basis as they are completed for individual patients. Data required for analysis of patients treated on this protocol will be maintained in a password-protected study-specific database. Data from the CRFs are keyed directly into the database by authorized research staff and verified on an ongoing basis.

### **14.1 TERMINATION OF STUDY**

Study accrual will terminate after the last participant has completed the final specimen collection described in this protocol. The study will continue until all samples are tested and the data is analyzed, which is expected to occur after approximately 2 years.

The PI may terminate the study at any time. The FDA, the IRB, or the US Office for Human Research Protections (OHRP) also have the authority to terminate the study should it be deemed necessary.

